F4. Review to detect presence or absence of hypoxemia indicative of ARDS: In order to further eliminate the unnecessary detailed record review, a focused review of the transfusion episode will be performed to detect hypoxemia occurring within six hours of completion of transfusion. Medical records will be reviewed for the respiratory status within six hours after the completion of the study unit transfusion to detect the following: Oxygen saturation (SpO2) less than 90% by pulse oxymetry without or with oxygen therapy; ratio of SpO2/FiO2 <315; and ratio of PaO2/FiO2 <300 on arterial blood gas analysis. FiO2 will be calculated for patients receiving oxygen by cannula or mask as follows: 1 liter = 0.21; 2 liters = 0.23; 3 liters = 0.25; 4 liters = 0.35; 6 and 7 liters = 0.45, and 8, 9, and 10 liters = 0.49 (Rice TW 2007).

If hypoxemia is documented, a detailed medical record review will be performed by the record review coordinator. The full extended data form will be completed. A Power Point summary of the major events and timeline will be prepared. The completed extended data forms and summaries will be sent to the Triage MD for further review.

Precise incidence rates for hypoxemia as defined in this manner in hospitalized patients are not available. Most of the data on incidence of acute respiratory failure (ARF) are reported in patients who are treated in the intensive care unit (ICU). For example, Flaatten et al have reported an incidence of ARF of 63% among 832 patients treated in the ICU. In 13,346 ICU admissions, 1,231 (9.2%) patients were found to have acute respiratory failure by Luhr et al. Pettila et al have described an incidence of ARF of 32.5% in 520 ICU patients while Vincent et al found that 32% of the 458 ICU patients had ARF at admission to the ICU and 35% of the 991 ICU patients developed ARF during their stay in ICU. Roupie et al report that 43% of the ICU patients required mechanical ventilation. A combined rate of 16% for ARDS and ALI in 1977 ICU admissions has been observed by Bersten et al. These data show a wide range for ARF in ICU patients. In order to be more conservative in our estimates for the number of charts requiring detailed review, we have estimated that 60% of the study patients would have hypoxemia/acute respiratory failure and would therefore require detailed chart review along with a review by a triage critical care physician (see below).

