A list of the components that were supplied to each participating hospital will then be printed by the blood center and provided to each corresponding transfusion service medical director or designated individual to identify corresponding recipients and to have the radiology and the medical records be abstracted by the record review coordinator(s). All information will be tracked and compiled into the tracking and data management systems either directly by research staff at the blood center/blood bank or by Westat, if forms are mailed to the coordinating center for data entry.

The coordinating center will be responsible for formation of the medical review board. The medical review board will assess all completed data forms in a blinded manner to determine the presence or absence of TRALI as described above. The coordinating center will compile the results of these reviews into the data management system to allow for formation of a database that will be used for analyses. The proposed diagnostic criteria for TRALI are detailed in the next section.

F25. Proposed Diagnostic criteria for TRALI: Using the Canadian Consensus Conference criteria, the medical review board will be responsible for reviewing the completed recipient forms and determining the presence or absence of TRALI (Kleinman et al).

- 1. New hypoxemia must be present and hypoxemia is defined as pO2/FiO2 ratio of <300 within 6 hours of completion of transfusion or venous oxygen saturation (SpO2) of less than 90% on room air; or other clinical evidence of hypoxemia (e.g., cyanosis). Based on the recent report from Rice TW et al., additional criteria to determine hypoxemia representative of ARDS will be included as follows: ratio of SpO2/FiO2 <315; where FiO2 will be calculated for patients receiving oxygen by cannula or mask as follows: 1 liter = 0.21; 2 liters = 0.23; 3 liters = 0.25; 4 liters = 0.3; 5 liters = 0.35; 6 and 7 liters = 0.45, and 8,9, and 10 liters = 0.49 (Rice TW 2007).
- 2. Bilateral infiltrates on frontal chest radiograph (obtained within 24 hours of Completion of transfusion) must be present. There must be absence of left atrial hypertension (i.e., circulatory overload). However, if ALI is diagnosed by the expert panel in the presence of left atrial hypertension, the case may be classified as TRALI/TACO (overlap case).

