- 3. For definition of left atrial hypertension, one or more of the following criteria must be present: EKG evidence for recent MI, echocardiogram indicative of heart failure or an ejection fraction <50%, a plasma troponin value greater than the upper reference range of the laboratory, a plasma brain natriuretic peptide of >100 pg/mL, pulmonary edema fluid/plasma fluid protein ratio less than 0.60, and pulmonary artery diastolic pressure or pulmonary artery wedge pressure of 18 mm Hg or more.

In addition to the above, clinical criteria for congestive heart failure, e.g., elevated jugular venous pressure, presence of S3 and S4 sound on auscultation, hepatojugular reflux, and excess input of fluid compared to output, and response to diuretic will be considered in order to differentiate TACO from TRALI.

- 4. No pre-existing acute lung injury before transfusion
- 5. No temporal relationship to an alternate risk factor for acute lung injury
 - Note: Recipients who meet the above criteria but also have a clear relationship to an alternate risk factor for acute lung injury will be considered to have possible TRALI. Also, in accordance with the NHLBI definition, such cases will be classified as TRALI with other risk factors for acute lung injury, provided that the expert panel determines that transfusion is the most likely cause of the ALI. ALI risk factors could be those that cause direct lung injury or those that cause indirect lung injury. Factors that cause direct lung injury are: aspiration, pneumonia, toxic inhalation, lung contusion, and near drowning. Factors that cause indirect lung injury are severe sepsis, shock, multiple trauma, acute pancreatitis, cardiopulmonary bypass, and drug overdose.

6. If the chest x-ray report review indicates absence of bilateral pulmonary infiltrates, the cases will be designated as "Not TRALI".

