
Estimate FiO2 as follows, if patient is receiving oxygen by nasal cannula or mask.

Room air: 0.21	1 Liter of O2: 0.23	2 Liters of O2: 0.25	3 Liters of O2: 0.27
4 Liters of O2: 0.30	5 Liters of O2: 0.35	6, 7 Liters of O2: 0.40	8, 9, 10 Liters of O2: 0.49

If receiving oxygen therapy with mechanical ventilation, use percent oxygen recorded on the patient's respiratory care data. Review ventilator data to find FiO2 value (eg. 405 oxygen administration equals a FiO2 of 0.4).

RESPIRATORY STATUS	YES	NO	NR
Oxygen saturation (SpO2) less than 90% by pulse oxymetry without oxygen therapy?			
Oxygen saturation (SpO2) less than 90% by pulse oxymetry while receiving oxygen therapy			
Ratio of SpO2/FiO2 <315 (See Note 1)			
Ratio of PaO2/FiO2 <300 (PaO2 = oxygen saturation on arterial blood gas analysis) (See Note 2)			

If answer to **ANY** of the above respiratory status items is **YES** then further chart review is required. If answer to **ALL** of the above respiratory status items is **NO** then stop now and send copy of form to Westat.

NO.	ITEM	YES	NO	NR	START DATE (If applicable)	RESOLVE DATE (If applicable)	NOTES
1	Acute CNS Injury (within 7 days before Tx)				applicable)	applicable)	Note 3
2	Acute renal failure (within 7 days before Tx)						Note 4
3	Aspiration						Note 5
4	Bone marrow stem cell transplant in past 12 months						
5	Burn as an admitting diagnosis (if within 48 hrs before reaction)						
6	Cancer or recent (within 1 month) chemotherapy						
7	Cardiac bypass during current admission (within 48 hrs before reaction)						
8	Cardiac ischemia during current admission (within 7 days before Tx)						
9	Hx of chronic alcohol abuse						Note 6
10	Hx of chronic renal failure						Note 7
11	Congestive heart failure during current admission (within 7 days before Tx)						Note 8
12	Hx of coronary artery disease						
13	Hx of diabetes mellitus						Note 9
14	DIC during current admission (within 7 days before Tx)						Note 10
15	Drug overdose as admitting diagnosis (within 48 hrs before reaction)						
16	Exposure to high altitude as admitting diagnosis (within 48 hrs before reaction)						
17	Heat stroke as admitting diagnosis (within 48 hrs before reaction)						
18	Hemorrhagic shock during current admission (within 48 hrs before reaction)						
19	High INR (>3.0) during current admission (within 7 days before Tx)						
20	Hx of immunosuppression						
21	Just underwent surgery (within 48 hours)						

SECTION F: PATIENT HISTORY & CLINICAL FINDINGS

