1	Post-transfusion fever ((temp above 100.4F or 38C) within 6 hrs				
2	Post-transfusion chills within 6 hrs without fever				
3	Acute hemolytic transfusion reactions within 24 hrs				
4	Delayed hemolytic transfusion reaction within 7 days				
5	Minor allergic (skin rash) within 6 hrs				
6	Severe allergic (anaphylactic) within 6 hrs				
7	Post-transfusion bacterial sepsis within 24 hrs				
8	Cardiac/fluid overload or congestive heart failure within 6 hrs				
9	Post-transfusion shortness of breath/dyspnea within 6 hrs				
10	Post-transfusion hypotension (systolic BP <90 mmHg) within 6 hrs				
11	Post-transfusion hypertension (systolic BP >140 mmHg) within 6 hrs				
12	Post-transfusion shock				
13	Post-transfusion O2 sat <90% on pulse oxymetry (SpO2) with or without O2 administration within 6 hrs				
14	Post transfusion ratio of SpO2/FiO2 <315 within 6 hrs				
15	Post-transfusion arterial blood gases within 6 hours after completion of transfusion showing pO2/FiO2 <300 mm Hg				
16	Post-transfusion lung auscultation reveals rales(crackles) within 24 hrs				
17	Post-transfusion lung auscultation reveals rhonchi within 24 hrs				
18	Post-transfusion elevated jugular venous pressure within 6 hrs				
19	Post-transfusion hepatojugular reflux detected within 6 hrs				

NO.	ITEM	YES	NO	NR	NOTES
20	Post-transfusion cyanosis within 6 hrs				
21	Post-transfusion central venous catheter measured elevated central venous pressure (>8 mm Hg) within 6 hrs				
22	Post-transfusion central catheter measured elevated pulmonary artery wedge pressure (>20 mm Hg) within 6 hrs				
23	Post-transfusion peripheral pitting edema detected within 24 hrs				
24	Post-transfusion, was there a loss of 4.5 kg weight in 72 hours after diuretic treatment				Note 22
25	Clinically suspect TRALI within 6 hrs				
26	Post-transfusion diagnosis of ARDS within 24 hrs				
27	Post-transfusion, patient required ICU admission within 24 hrs				Note 23
28	Post-transfusion, required vasopressures to support blood pressure within 24 hrs (e.g., dopamine, norepinephrine, epinephrine)				
29	Rapid resolution of lung infiltrates on chest X-ray after diuresis or dialysis within 6 hrs				

SECTION K: OTHER BLOOD COMPONENTS AND FLUID ADMINISTRATION

NO.	COMPONENT/FLUID	PRE-Tx AMOUNT (24 hour before Tx of the study unit started) Record if applicable	POST-Tx AMOUNT (24 hours after the Tx of the study unit finished) Record if applicable
1	RED BLOOD CELLS (No. of Units)		
2	PLATELETS, WHOLE BLOOD (No. of units)		

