Note 14: If patient received any RBC transfusion for drop in hemoglobin or hematocrit, select "yes".

Note 15: Extubation date/time should be recorded when the extubation is performed and note that this time may occur beyond the 24-48 hours after the transfusion. If intubation was performed and extubation did not take place (e.g. patient was discharged to a chronic ventilatory care facility while intubated), record No. If no record exists to determine the date/time of intubation, record NR.

Note 16: Calculate the excess fluids administered by fluids given (oral or intravenous) minus fluid losses (urine, gastric suction, thoracic or abdominal drainaige) in 24 hours prior to the transfusion. Write down the amount of excess fluid in mL.

Note 17: Pre-transfusion bacterial sepsis: If MD or nursing note indicates possibility of sepsis or a diagnosis of sepsis; other manifestations include a focus of infection (e.g. pneumonia, cellulitis, skin lucer, wound infection); manifestations of inflammation (e.g. fever, tachycardia, tachypnea), and shock (BP less than 90 mmHg systolic; sweating, cold clammy skin). Laboratory test may also show positive blood culture.

Note 18: Pre-transfusion shock: MD or nursing note indicating presence of shock. Manifestations include low systolic BP (<90 mmHg), tachycardia, cold clammy skin, distal extremity cyanosis, low urine output, mental confusion or somnolence.

Note 19: Calculate ratio by dividing the percent saturation of oxygen on pulse oxy (SO2) by FiO2 (calculate FiO2 as follows: room air = 0.21; one liter oxygen = 0.23; 2 liters = 0.25; 3 liters = 0.27; 4 liters = 0.3, 5 liters = 0.35; 6 & 7 liters = 0.4; and 8-10 liters = 0.49. Example: If oxygen saturation is 90% on 4 liters of oxygen by face mask, then the ratio is 90/0.3 = 300.

Note 20: PF ratio. Calculate by dividing the pO2 (on arterial blood gases) by FiO2 (flow rate of oxygen in decimel of 1.0, e.g., 40% FiO2 = 0.4). Example: Someone with pO2 of 120 receiving 40% oxygen, the PF ratio is $120 \div 0.4 = 300$.

Note 21: The definition of when the reaction occurred is the earliest time at which one or more of the following events were noted: pO2/FiO2 <300; SO2/FiO2 <315, and pulmonary edema on chest x-ray.

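### The protocol's oxygen-flow to FiO2 conversions and wedge-pressure cut-offs conflict between F4, F25 and Appendix G, so in limited ranges the same readings can meet or fail the written TRALI criteria

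*Protocol*

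**What the plan says.** Three places convert oxygen flow to FiO2.

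- **F4 (screening for hypoxemia):** "1 liter = 0.21; 2 liters = 0.23; 3 liters = 0.25; 4 liters = 0.35; 6 and 7 liters = 0.45", then 0.49 at 8-10 L. There is no entry for 5 L.
- **F25 item 1 (diagnostic criteria):** "1 liter = 0.21; 2 liters = 0.23; 3 liters = 0.25; 4 liters = 0.3; 5 liters = 0.35", continuing "6 and 7 liters = 0.45, and 8,9, and 10 liters = 0.49". F25 attaches this list to the SpO2/FiO2 criterion. F4 and F25 cite the same source.
- **Appendix G (the form coordinators complete):** Note 19 has "one liter oxygen = 0.23; 2 liters = 0.25; 3 liters = 0.27; 4 liters = 0.3", and Section E has "6, 7 Liters of O2: 0.40". Section E and Note 19 agree with each other.

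The screening thresholds in F4 and Section E are SpO2 below 90% with or without oxygen, SpO2/FiO2 below 315, and PaO2/FiO2 below 300. On the form, any YES sends the chart on and all NO ends the review. F25 uses the same two ratios, restricts the SpO2 below 90% criterion to room air, and lets other clinical signs of low oxygen count.

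For left atrial hypertension, which must be absent for TRALI, F25 item 3 includes "pulmonary artery wedge pressure of 18 mm Hg or more". The form asks "Post-transfusion central catheter measured elevated pulmonary artery wedge pressure (>20 mm Hg) within 6 hrs" as a YES/NO/NR item in Section J, and uses the same cut-off before transfusion in Section H. Neither section has a column for the measured value.

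**The concern.** The conversion is part of the endpoint definition, because it fixes the PaO2 or SpO2 at which a patient on oxygen counts as hypoxemic. Under F18 coordinators work on the form, while F25 tells the Medical Board how to diagnose. If the two convert differently, the same readings can satisfy one and fail the other.

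The stop rule makes this hard to repair. Section E records only YES/NO/NR. Blood gases (Section O) and highest FiO2 (Section G) come later, so they need not exist for a stopped chart. No section has a field for the SpO2 value or for oxygen flow. Section E also describes PaO2 as an oxygen saturation, although Note 20 uses pO2.

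The study expects about 40 TRALI cases (30 and 10 in F23), and the Appendix H sample-size review uses the blinded incidence. A few cases lost or added would therefore matter.

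**Working it through.** **Inputs.** FiO2 by flow, as printed:

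| Flow | F4 | F25 | Appendix G |
|---|---|---|---|
| 1 L | 0.21 | 0.21 | 0.23 |
| 2 L | 0.23 | 0.23 | 0.25 |
| 3 L | 0.25 | 0.25 | 0.27 |
| 4 L | 0.35 | 0.30 | 0.30 |
| 5 L | none | 0.35 | 0.35 |
| 6-7 L | 0.45 | 0.45 | 0.40 |
| 8-10 L | 0.49 | 0.49 | 0.49 |

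**The plan's own figure.** Note 19's worked example, saturation 90% on 4 L, is 90/0.30 = 300. It reproduces.

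**Implied cut-offs.** PaO2/FiO2 < 300 means PaO2 < 300 × FiO2. SpO2/FiO2 < 315 means SpO2 < 315 × FiO2.

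- 1/2/3 L, PaO2 below: 63/69/75 (F4) against 69/75/81 (form).
- 1/2/3 L, SpO2 below: 66.2/72.5/78.8% (F4, F25) against 72.5/78.8/85.1% (form).
- 4 L, PaO2 below: 105 (F4) against 90 (form).
- 4 L, SpO2: always met under F4 (100/0.35 = 286 < 315), against below 94.5% (F25, form).

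**Stop rule at 1-3 L.** The SpO2 cut-offs all lie below 90%, and SpO2 below 90% already passes the chart on. Only PaO2/FiO2 can change the result, and only when SpO2 is 90% or more. Example: 2 L, PaO2 72, SpO2 94%.

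- F4: 72/0.23 = 313 and 94/0.23 = 409, so not hypoxemic.
- Form: 72/0.25 = 288 and 94/0.25 = 376, so hypoxemic through PaO2/FiO2.

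**Stop rule at 4 L.** Example: SpO2 97%, PaO2 95.

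- F4: 97/0.35 = 277 and 95/0.35 = 271, so review continues.
- Form: 97/0.30 = 323 and 95/0.30 = 317, so review stops.

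**F25's SpO2/FiO2 criterion.** Example: 3 L, SpO2 82%. The chart passes screening under either table because SpO2 is below 90%.

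- F25's FiO2: 82/0.25 = 328, not met.
- Form's FiO2: 82/0.27 = 304, met.

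**6-7 L.** The largest possible SpO2/FiO2 is 100/0.45 = 222 or 100/0.40 = 250. Both are below 315, so with SpO2 recorded the patient is hypoxemic under every table.

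**PaO2 label.** Illustration with assumed values: room air, PaO2 62, saturation 91%. The true ratio is 62/0.21 = 295, a YES. Entering the saturation, as the label suggests, gives 91/0.21 = 433. Every item is then NO and review stops.

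**Wedge pressure.** Whole-number readings of 18, 19 and 20 mm Hg meet F25 and are NO on the form.

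**The case against.** The strongest reply is that practice may be more uniform than the text. Coordinators use one form, which prints one consistent table twice. Training is shared, a single triage physician serves all centers, and one Board adjudicates. This stands against any inference that classification would vary by center; the documents give no support for that.

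F4's 4 L entry may be a dropped phrase. Losing the 4 L value and the 5 L label from F25's list, in typing or in reading the PDF, yields exactly F4's text. Restoring them removes the 4 L example and makes F4 equal to F25. Both would still differ from the form at 1, 2, 3 and 6-7 L.

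F25 ties its list to SpO2/FiO2, so the PaO2/FiO2 contrast at 1-3 L runs between F4 and the form. There the form admits more charts than F4, so that particular difference loses no cases at screening.

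At 6-7 L a reader might infer that PaO2 of 120-135 flips the classification. It does so only if a blood gas exists without any SpO2. A reader might also tie the pilot's hypoxemia fractions (F6) to this conflict, but F6 does not say which conversion was used.

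Section O does record FiO2 and PaO2, but only for charts that continue. Note 20 does define the PaO2 ratio correctly, so Section E's label is a wording error, though one inside a stop rule. Wedge pressure is one of several alternatives for left atrial hypertension, and the case summary may show the reading.

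**Conclusion.** The contradiction is real and sits in decision thresholds. F4 and F25 disagree with the form at 1-3 L and 6-7 L, F4 disagrees with both at 4 L and omits 5 L, and the wedge cut-offs disagree for readings of 18-20 mm Hg.

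The consequences are narrower than the list of differences suggests. At the stop rule they are confined to 6 mm Hg bands of PaO2 at 1-3 L with SpO2 of 90% or more, and to 4 L if F4's value is as intended. For F25 they affect SpO2/FiO2 at 1-3 L, and a final diagnosis only where PaO2/FiO2 and other clinical signs do not settle the matter. The stop-rule examples assume that one FiO2 serves both ratios, as in F4 and the form.

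A reader might infer bias between the antibody-positive and antibody-negative groups. The documents do not support that: the local investigator, the triage physician and the Board are all blinded. Nor do the tables mechanically fix the panel's diagnosis. What remains is non-directional misclassification whose size cannot be derived from the protocol, and which cannot be corrected afterwards for stopped charts. The documents do not establish which conversion or wedge cut-off is right, and none is chosen here.

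**What to change.** 1. Reconcile F4, F25 item 1, Appendix G Section E and Note 19 to one conversion table, checked against the cited source and printed identically with an entry for every flow. State whether it applies to both SpO2/FiO2 and PaO2/FiO2.
2. In Section E, before the stop, record SpO2, PaO2 and oxygen flow or FiO2 as numbers, so that the coordinating center computes the ratios.
3. Correct Section E's description of PaO2 so that it agrees with Note 20.
4. Reconcile the wedge-pressure cut-off between F25 item 3 and form Sections H and J, and record the measured value.

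The cost is a text correction and a few extra numeric fields. Abstraction takes slightly longer for charts that now stop at Section E. The changes are cheap before data collection; afterwards, re-classifying a stopped chart would mean returning to the hospital record.
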